8.3.6 SERIOUS ADVERSE EVENT REPORTING

The study clinician will immediately report to the sponsor and MMS Pharmacovigilance, per the SAE reporting form, any serious adverse event, whether or not considered study intervention related, including those listed in the protocol or investigator brochure and must include an assessment of whether there is a reasonable possibility that the study intervention caused the event. Study endpoints that are serious adverse events (e.g., all-cause mortality) must be reported in accordance with the protocol unless there is evidence suggesting a causal relationship between the study intervention and the event (e.g., death from anaphylaxis). In that case, the investigator must immediately report the event to the sponsor.

All serious adverse events (SAEs) will be followed until satisfactory resolution or until the site investigator deems the event to be chronic or the participant is stable. Other supporting documentation of the event may be requested by Emory University/[REDACTED] or MMS Pharmacovigilance and should be provided as soon as possible.

The study sponsor (Emory) will be responsible for notifying the Food and Drug Administration (FDA) of any unexpected fatal or life-threatening suspected adverse reaction as soon as possible, but in no case later than 7 calendar days after the sponsor's initial receipt of the information. In addition, the sponsor must notify FDA and all participating investigators in an Investigational New Drug (IND) safety report of

potential serious risks, from clinical trials or any other source, as soon as possible, but in no case later than 15 calendar days after the sponsor determines that the information qualifies for reporting.

8.3.7 REPORTING EVENTS TO PARTICIPANTS

N/A

8.3.8 EVENTS OF SPECIAL INTEREST

N/A

8.3.9 REPORTING OF PREGNANCY

If a participant becomes pregnant, the study drug will be discontinued immediately while continuing to carry out safety follow-up. Permission will be requested to follow the pregnant women to pregnancy outcome. All pregnancies should be reported as an adverse event and the reporting mechanisms under that apply.

8.3.10 DRUG-INDUCED LIVER INJURY CLINICAL MANAGEMENT PLAN

If subjects develop elevations of AST or ALT >2x baseline or total bilirubin >1.5x baseline values during the study, repeat testing will be performed within 48 -72 hours. If there are persistent elevations (ALT or AST >2 X baseline or TBL >1.5 X baseline values) upon repeat testing, then close observation (testing and physical examination 2-3 times per week) will be implemented and discontinuation of drug will be considered.

A decision to discontinue or temporarily interrupt the study drug will be based on factors that include how much higher than baseline ALT and AST were relative to the upper limit of normal (ULN) and how much the on study ALT and AST levels have increased relative to baseline, in addition to whether there is concomitant elevation of bilirubin or INR.

The study drug will be discontinued or temporarily interrupted:

- If baseline measurements (BLM) were <2 X ULN, discontinue if ALT or AST increases to >5 X BLM.
- If BLM \geq 2 X ULN but <5 X ULN, discontinue if ALT or AST increases to >3 X BLM.
- Discontinue if ALT or AST increase is >2 X BLM AND the increase is accompanied by a concomitant increase in TBL to >2 X BLM OR the INR concomitantly increases by > 0.2.
- In any subjects with signs and symptoms of fatigue, nausea, vomiting, right upper quadrant pain or tenderness, fever, rash, and/or eosinophilia (> 5%).

If a patient lives in a remote area, laboratory testing will be performed locally and the results will be promptly communicated to the investigator site.

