4.2 SCIENTIFIC RATIONALE FOR STUDY DESIGN

The scientific rationale for this phase 2a, open label trial in children with NAFLD is based on critical factors emanating from both the disease and the investigational product. NAFLD trials are challenging because of the large placebo response rate, estimated to be from 20-40%. The placebo response is likely in part due to response to lifestyle changes (improved diet and increased exercise) which is co administered in most trials. A placebo-controlled trial would require a much larger sample size (~140 subjects) in order to test response of ALT in gemcabene compared to placebo. Because this is the first study in children, a smaller study design was selected – an open label single arm study. The problem of placebo response is managed in two ways. First, the sample size was made large enough to allow detection of a greater than historical placebo response rate. Second, there will be a 4-6 week dietary lead in period between screening and initiation of gemcabene (baseline). This will moderate the effects of the dietary and exercise changes in response to counseling.

Children ages 12 years and older were selected for this study because there is not yet juvenile toxicity data to support testing in younger children.

Children diagnosed with NAFLD by either liver biopsy or by MRI will be included because routine clinical practice is quickly moving away from the use of liver biopsies with the advent of easily accessible and accurate MRI based hepatic fat measurement. To ensure that very mild cases of NAFLD are not

included, children must have an elevated ALT 2 x ULN (≥ 54 U/L for boys and ≥ 46 U/L for girls) at the time of screening (demonstrating increased likelihood of ongoing inflammation in the liver). To assess inflammation change in historical ALT (within three months prior to screening) will be obtained (if available). If the ALT at screening is more than two times the historic value, or there is no historic value available, the subject will be asked to repeat the screening ALT after four weeks. If the repeat ALT is greater than 50% increased or decreased over the screening ALT a third ALT will be obtained. If a third ALT is not within 50% of the previous value the subject may be re-screened at a later date.

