5 STUDY POPULATION

5.1 INCLUSION CRITERIA

In order to be eligible to participate in this study, an individual must meet all of the following criteria:

1. Provision of signed and dated informed consent form
2. Provision of signed and dated assent, if indicated
3. Stated willingness to comply with all study procedures and availability for the duration of the study
4. Children aged 12-17 years at the time of informed consent
5. History of clinical diagnosis of NAFLD including a, b and c below:
 - a. Medical history eliminating, other chronic liver diseases (for example mitochondrial diseases, hepatotoxic drugs, anorexia nervosa)
 - b. Laboratory studies: negative testing for hepatitis C and normal ceruloplasmin
 - c. Either liver biopsy confirming NAFLD or MRI $> 10\%$ steatosis within the past three years
6. ALT ≥ 54 U/L for boys or ≥ 46 U/L for girls and ≤ 250 U/L at screening visit and within past three months (prior to screening). If ALT at screening is more than two times the historic value (or a historic value is not available), the subject will be asked to repeat the ALT after four weeks. If

the repeat ALT is more than 50% increased or decreased over the screening ALT a third ALT may be obtained. If a third ALT is not within 50% of the previous value then the subject is ineligible, but may be rescreened at a later date.

7. Body weight \geq 60 kg at the time of screening
8. Able to take oral medication and be willing to adhere to the GEM-IIT-601 regimen
9. Minimum of three months of attempted lifestyle modification to treat the NAFLD and agreement to adhere to Lifestyle Considerations (see section 5.3) throughout study duration

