8.2 SAFETY AND OTHER ASSESSMENTS

Specific Safety Measures:

Hemoglobin decrease

For a hemoglobin decrease of > 1.5 g/dL from baseline during the study, repeat hematology studies and reflexive evaluation of reticulocyte count will be performed. The subject's past medical history, concomitant medications (including over the counter drugs and herbal supplements), and any recent symptoms (e.g., bleeding, shortness of breath, fatigue) will be reviewed to determine a potential etiology and make a clinical assessment of the significance of the finding.

Creatinine increase

If, at any visit, a creatinine increase of > 0.3 mg/dL (27 µmol/L) from baseline, a GFR decrease of >15 mL/min from baseline is observed, a repeat chemistry/urinalysis will be performed within seven days. The subject's past medical history, concomitant medications (including over the counter drugs and herbal supplements), and any recent symptoms (e.g., fatigue, malaise, polyuria/oliguria, or palpitations) will be reviewed to determine a potential etiology and make a clinical assessment of the significance of the finding.

Possible muscle and liver injury

For muscle injury, CPK, hepatic, and renal function laboratory data will be integrated with myopathy signs and symptoms.

For liver injury, laboratory data will be integrated with hepatic signs and symptoms. Alanine aminotransferase increases > 2 × baseline with symptoms of hepatitis or > 3 × baseline with or without symptoms of hepatitis will be evaluated and managed according to guidelines for studies in patients with pre-existing liver disease. This includes a repeat assessment as soon as possible to confirm the findings and a clinical evaluation. If the participant has signs or symptoms of hepatitis or ALT > 5x baseline, the study drug will be temporarily discontinued.

Data to be provided to the participants – At a minimum, the locally run clinical labs and MRI liver fat result from baseline will be provided to each patient at the end of the study and reviewed with them by a study investigator. This includes the CMP, CBC, GGT, hemoglobin A1c, insulin, glucose and fasting lipids. The investigator may choose to share other locally run clinical labs from other time points with the participant.

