10.1.2 STUDY DISCONTINUATION AND CLOSURE

This study may be temporarily suspended or prematurely terminated if there is sufficient reasonable cause. The DSMB will review all AEs and SAEs and may suspend or terminate the study for safety concerns. AEs will be reviewed quarterly and for any SAE, an ad hoc meeting of the DSMB will be convened within 10 business days to review the event.

Written notification, documenting the reason for study suspension or termination, will be provided by the suspending or terminating party to study participants, investigators, Gemphire, the Investigational New Drug (IND) sponsor and regulatory authorities. If the study is prematurely terminated or suspended, the Principal Investigator (PI) will promptly inform study participants, the Institutional Review Board (IRB), and sponsor and will provide the reason(s) for the termination or suspension. Study participants will be contacted, as applicable, and be informed of changes to study visit schedule.

Circumstances that may warrant termination or suspension include, but are not limited to:

- Determination of unexpected, significant, or unacceptable risk to participants
- Demonstration of efficacy that would warrant stopping
- Insufficient compliance to protocol requirements
- Data that are not sufficiently complete and/or evaluable
- Determination that the primary endpoint has been met
- Determination of futility

Study may resume once concerns about safety, protocol compliance, and data quality are addressed, and satisfy the sponsor, IRB and/or Food and Drug Administration (FDA).

Patient-specific trial stopping rules include:

- In any patient who develops an AE of grade 3 that is probably or possibly related to study drug and any patient who develops a grade 4 or higher CTCAE regardless of causality assessment, investigational product will be discontinued.
- Hemoglobin will be assessed by central laboratory evaluation. For a hemoglobin decrease of > 1.5 g/dL from baseline during the study, repeat hematology studies and reflexive evaluation of reticulocyte count will be performed. The patient's past medical history, concomitant medications (including over the counter drugs and herbal supplements), and any recent symptoms (e.g., bleeding, shortness of breath, fatigue) will be reviewed to determine a potential etiology and make a clinical assessment of the significance of the finding.

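### Section 8.3.10 has no enzyme-only stopping limit for baseline ALT or AST of 5 x ULN or more, although children with screening ALT up to 250 U/L are eligible

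*Combined protocol and SAP*

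**What the plan says.** Section 8.3.10 lists when study drug is stopped or interrupted for liver findings. Two entries depend on enzymes alone. With baseline below 2 x ULN, the limit is ALT or AST above 5 x baseline. The second entry covers baselines of at least 2 x "ULN but <5 X ULN, discontinue if ALT or AST increases to >3 X BLM". The remaining entries need a bilirubin or INR rise alongside an enzyme rise above 2 x baseline, or symptoms or eosinophilia.

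On who can enter, section 4.2 states that "children must have an elevated ALT 2 x ULN" and gives this as 54 U/L for boys and 46 U/L for girls. Criterion 6 in section 5.1 sets the ceiling at "250 U/L at screening visit and within past three months". No ceiling is set for the baseline value itself.

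Other rules apply at every baseline:
- Section 8.3.10: above 2 x baseline, "repeat testing will be performed within 48 -72 hours". If the rise persists, the child is tested and examined two to three times a week and stopping is to be considered. The same section makes baseline severity relative to ULN one of the factors in that decision.
- Section 8.2: ALT above 3 x baseline "will be evaluated and managed according to guidelines for studies in patients with pre-existing liver disease". With hepatitis signs or symptoms, or "ALT > 5x baseline, the study drug will be temporarily discontinued".
- Section 10.1.2: drug stops for a grade 3 event probably or possibly related to it, and for "any patient who develops a grade 4 or higher CTCAE regardless of causality assessment, investigational product will be discontinued".

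**The concern.** The second bracket is closed at the top and no third one follows, yet the entry criteria admit children above it. For an isolated ALT rise of between 3 x and 5 x baseline, a child just below 5 x ULN meets a numeric limit in section 8.3.10. A child just above it, with the more abnormal liver, does not. Handling of that child rests on guidelines the protocol does not reproduce, on investigator judgement and on CTCAE grading. The next fixed multiple is 5, so the stated multiples run from 5 to 3 and back to 5 as baseline rises.

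The section 8.2 hold names only ALT. An isolated AST rise from a high AST baseline therefore has no fixed baseline-multiple limit. How many children that touches cannot be said, because no AST ULN or AST entry range is given.

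Prior human data are reassuring. Section 2.3.1 reports one patient above 3 x ULN, on 600 mg with atorvastatin 80 mg, and elevations overall similar to placebo. But those data are from adults, and section 2.2 states that no earlier study was in NAFLD, so they do not show how often the gap would be met here.

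**Working it through.** **Inputs.** 2 x ULN = 54 U/L (boys) and 46 U/L (girls), section 4.2. Highest admitted screening ALT = 250 U/L, section 5.1. Limits of >5 x and >3 x baseline for the two brackets, section 8.3.10. Hold at >5 x baseline, ALT only, section 8.2.

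**1. Where the brackets end.**
- ULN = 54/2 = 27 and 46/2 = 23 U/L.
- 5 x ULN = 135 U/L (boys) and 115 U/L (girls).
- Entry ceiling in ULN units: 250/27 = 9.3 and 250/23 = 10.9. Section 2.1 gives normal ALT in boys as below 26 U/L; with that figure, 250/26 = 9.6.

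On this scale, baselines of 135 to 250 U/L (boys) and 115 to 250 U/L (girls) have no enzyme-only limit in section 8.3.10. Because 250 U/L caps screening and not baseline, a baseline can be higher still.

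**2. The fixed limit on either side of the boundary (U/L).** Below 5 x ULN it is 3 x baseline (8.3.10); above, 5 x baseline (8.2). The last column shows the limit if the 3 x rule continued upward.

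| Child | Baseline | Limit as written | In ULN | If 3 x continued |
|---|---|---|---|---|
| Boy | 134 | 3 x 134 = 402 | 402/27 = 14.9 | – |
| Boy | 136 | 5 x 136 = 680 | 680/27 = 25.2 | 3 x 136 = 408 |
| Boy | 250 | 5 x 250 = 1250 | 1250/27 = 46.3 | 3 x 250 = 750 (27.8 x ULN) |
| Girl | 114 | 3 x 114 = 342 | 342/23 = 14.9 | – |
| Girl | 116 | 5 x 116 = 580 | 580/23 = 25.2 | 3 x 116 = 348 |
| Girl | 250 | 5 x 250 = 1250 | 1250/23 = 54.3 | 3 x 250 = 750 (32.6 x ULN) |

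A 2 U/L difference in baseline at the boundary moves the limit by 680 − 402 = 278 U/L for boys and 580 − 342 = 238 U/L for girls.

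**3. Sensitivity to the ULN.** Section 8.3.10 does not say which ULN applies, and safety ALT is run at local laboratories (section 8.1). Uncovered share of the admitted screening range = (250 − 5 x ULN)/(250 − entry floor), with floors 54 and 46. The single ULNs of 30 to 50 U/L are assumptions.

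| ULN (U/L) | Boys | Girls |
|---|---|---|
| 27 / 23 (section 4.2) | 115/196 = 58.7% | 135/204 = 66.2% |
| 30 | 51.0% | 49.0% |
| 35 | 38.3% | 36.8% |
| 40 | 25.5% | 24.5% |
| 45 | 12.8% | 12.3% |
| 50 | 0% | 0% |

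Every admitted screening value falls inside a bracket once ULN exceeds 250/5 = 50 U/L. These are widths of the ALT range, not proportions of children; the documents give no ALT distribution.

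**The case against.** The missing bracket is not really in dispute; its consequence is. The strongest points are these.

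- **Other rules may act first.** The CTCAE rule in section 10.1.2 applies at every baseline, and the guidelines invoked by section 8.2 at more than 3 x might cover this bracket. This stands as a limit on the conclusion: it cannot be shown that 5 x is ever the operative stop. Nor can the reverse be shown, since the documents give neither the CTCAE cut-offs nor the guidelines.
- **Monitoring is substantial.** Prompt retesting, close observation, the bilirubin/INR and symptom rules, investigator withdrawal and DSMB review all apply. This is correct and lowers the practical risk. It does not supply a fixed enzyme-only limit, which the plan thought worth having just below 5 x ULN.
- **The tightening from 5 x to 3 x is largely notional for ALT.** On the section 4.2 scale, entry already requires 2 x ULN at screening, so few children should fall in the first bracket, and the section 8.2 hold is a general backstop, not a looser limit written for high baselines. This is fair. The discontinuity at 5 x ULN does not depend on it.
- **Section 8.3.10 leaves the choice between stopping and interrupting open even below 5 x ULN.** True, but one or the other is still required there.
- **A flat 3 x limit is partly preference.** At baseline 250 it still permits 750 U/L, and nothing in the documents shows that 3 x is better than a stricter multiple. This stands too. Extending 3 x is simply the smallest change that removes the step.

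**Conclusion.** The concern holds, limited to this: the numeric 3 x limit for baselines of 2 to under 5 x ULN does not continue to higher baselines that the entry criteria admit, and the only fixed multiple left there is 5 x, for ALT alone. Confidence is high on the missing text and the arithmetic. Confidence cannot be high on how often it would matter, because the number of children above the bracket is unknown and other rules may stop drug sooner.

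The size rests on the ULN of 27 and 23 U/L implied by section 4.2. A higher local ULN shrinks the gap. It should be fixed: as written, the most abnormal eligible livers get the looser stated limit, in a first paediatric study of the drug, and the correction is cheap.

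**What to change.** 1. In section 8.3.10, open the second bracket at the top so that it reads BLM ≥ 2 x ULN. The limit of more than 3 x baseline for ALT or AST then covers all higher baselines.
2. In section 8.2, make the sentence on the hold at more than 5 x baseline defer to section 8.3.10 and cover AST.
3. In section 8.3.10, name the ULN to be used: the sex-specific ALT values implied by section 4.2, and an AST value, which the protocol does not currently give.

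The cost is one edited bracket, one aligned sentence and one definition in a protocol amendment. No new tests are needed, since ALT and AST are already in the local metabolic panel at Baseline and Weeks 2, 6 and 12. The downside is that some high-baseline children may have drug interrupted earlier: at baseline 250 U/L, above 750 instead of 1250 U/L on the baseline-multiple limit.

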monkeys, over 26 weeks at >30 mg/kg/day fatty changes were seen in the liver and kidneys. Carcinogenicity studies are ongoing in mice and rats. No mutagenic effects were seen in genetic toxicity studies. Developmental toxicity studies demonstrated abnormalities and teratogenicity at doses >10 mg/kg/day in rats but none in rabbits.

Summary of clinical studies with Gemcabene from the Investigator Brochure Version 2:

Phase 1 PK studies have demonstrated that oral gemcabene is rapidly absorbed with exposure increasing approximately linearly with dose. The primary route of elimination is renal. There is no clinically relevant effect on QT interval. There was a rapidly reversible increase in serum creatinine that is thought to be a hemodynamic change rather than a direct nephrotoxic effect because no change in protein to creatinine ration and no abnormal urine analysis was present. No effect was observed on blood pressure. There was an increase in the glucose disposal rate.

Phase 2 Efficacy studies have demonstrated benefits. In patients with dyslipidemia, monotherapy with 300 – 900 mg significantly lowered LDL-C compared to placebo in three Phase 2 studies. In patients with baseline TG \geq 200 mg/dL (Study 1027-04), gemcabene lowered TG by 39% at the 300 mg dose compared with 5% lowering by placebo.

Human safety data is drawn from this collection of 19 clinical studies. The most frequent reported adverse events in healthy volunteers for single doses were headache, asthenia, nausea, dizziness and somnolence. The most frequent adverse events for 4 weeks were headache, infection, nausea, asthenia, photosensitivity reaction, rhinitis, diarrhea, flatulence, dizziness and pharyngitis. In patients with dyslipidemia treated for 8 weeks, headache, asthenia, dizziness and pain were more frequent with gemcabene compared to placebo at doses from 300-900 mg. Nausea, dyspepsia and flatulence were more frequent with gemcabene compared to placebo. In 1272 healthy adult volunteers and patients, only 17 discontinued due to gemcabene related adverse events. There were no treatment related serious adverse events and no deaths.

Important Literature and Data Relevant to the Trial

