5.2 EXCLUSION CRITERIA

An individual who meets any of the following criteria will be excluded from participation in this study:

1. Heart disease (e.g., myocardial infarction, heart failure, unstable arrhythmias)
2. Seizure disorder
3. Active coagulopathy (INR $>$ 1.4)
4. Renal dysfunction with an estimated glomerular filtration rate (eGFR) $<$ 60ml/min/1.73 calculated using Schwartz Bedside GFR calculator for children
5. History of active malignant disease requiring chemotherapy or radiation
6. History of significant alcohol intake (AUDIT questionnaire) or inability to quantify alcohol consumption
7. Use of new medications or supplements with the intent to treat NAFLD/NASH during the 30 days prior to screening, including statin therapy. Medications or supplements (including metformin and vitamin E) that they have been on and are on a stable dose are acceptable
8. History of bariatric surgery or planning to undergo bariatric surgery during study duration
9. Clinically significant depression
10. Any girl nursing, planning a pregnancy, known or suspected to be pregnant, or who has a positive pregnancy screen
11. Non-compensated liver disease defined as cirrhosis and any one of the following hematologic, biochemical, and serological criteria on entry into protocol:
 - Hemoglobin $<$ 10 g/dL;
 - White blood cell (WBC) $<$ 3,500 cells/mm³;
 - Neutrophil count $<$ 1,500 cells/mm³;
 - Platelets $<$ 150,000 cells/mm³;
 - Total bilirubin $>$ 1.3 mg/dL unless due to Gilbert's syndrome (subjects with a history of Gilbert's syndrome may be included if both direct bilirubin and the reticulocyte count do not exceed the ULN [reflexive direct bilirubin testing will be used to confirm Gilbert's syndrome])
 - Albumin $<$ 3.2 g/dL
 - International normalized ratio (INR) $>$ 1.3
 - Abnormal alkaline phosphatase
 - Any history of ascites, variceal bleeding, hepatic encephalopathy, or hepatocellular carcinoma (HCC)
12. Poorly controlled diabetes mellitus (hemoglobin A1c (HbA1c) $>$ 8%) or requiring insulin
13. Patients with type I diabetes mellitus
14. Chronic liver disease other than NAFLD
15. Patients on CYP 3A4 inhibitors such as itraconazole or macrolide antibiotics are excluded
16. Patients who are on thiazolidinediones, fibrates or fish oils are excluded

17. Patients who are on daily prescription medications are excluded except for allergy medications, ADHD medications, asthma medications, or any other acceptable medication in the opinion of the investigator

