7.2 PARTICIPANT DISCONTINUATION/WITHDRAWAL FROM THE STUDY

Participants are free to withdraw from participation in the study at any time upon request.

An investigator may discontinue or withdraw a participant from the study for the following reasons:

- Pregnancy
- Significant study intervention non-compliance
- If any clinical adverse event (AE), laboratory abnormality, or other medical condition or situation occurs such that continued participation in the study would not be in the best interest of the participant
- Disease progression which requires discontinuation of the study intervention

- If the participant meets an exclusion criterion (either newly developed or not previously recognized) that precludes further study participation
- Participant unable to receive gemcabene for ≥ 14 days.

The reason for participant discontinuation or withdrawal from the study will be recorded on the Case Report Form (CRF). Subjects who sign the informed consent form but do not receive the study intervention may be replaced. Subjects who sign the informed consent form, receive the study intervention for > 4 weeks, and subsequently withdraw, or are withdrawn or discontinued from the study, will not be replaced.

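### The symptom bullet of the liver-injury plan (8.3.10) has no enzyme, severity or causality condition and does not match 8.2 or 10.1.2, so one mild symptom can bring different dosing instructions

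*Combined protocol and SAP*

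**What the plan says.** The list in 8.3.10 opens with "The study drug will be discontinued or temporarily interrupted". Its first two bullets use ALT or AST multiples of baseline that depend on the starting level. The third begins "Discontinue if ALT or AST increase is >2 X BLM AND the increase is accompanied by a concomitant increase in TBL", with an INR rise as the alternative companion sign. The fourth is "In any subjects with signs and symptoms of fatigue, nausea, vomiting, right upper quadrant pain or tenderness, fever, rash", and ends "and/or eosinophilia (> 5" percent).

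Three other places bear on the same decision:

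- **8.3.10, text before the list.** Repeat testing starts at AST or ALT above 2 times baseline or bilirubin above 1.5 times baseline. The decision to stop or interrupt is said to rest on factors that include the ALT and AST rise, bilirubin and INR.
- **8.2, possible liver injury.** "If the participant has signs or symptoms of hepatitis or ALT > 5x baseline, the study drug will be temporarily discontinued".
- **10.1.2, patient-specific stopping rules.** Drug is stopped for a grade 3 adverse event judged probably or possibly related, or for grade 4 or higher whatever the cause.

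On the drug's known effects, 2.2 reports: "Nausea, dyspepsia and flatulence were more frequent with gemcabene compared to placebo". Section 2.3.1 also lists nausea among the common adverse events.

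**The concern.** The fourth bullet stands under a mandatory lead-in, and its and/or wording makes any single item sufficient. It does not separate a symptom that accompanies a liver signal from one that does not, or a new symptom from one present before the first dose. Fatigue, for instance, is measured at Baseline by a PROMIS form, yet the bullet exempts no pre-existing fatigue.

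A site that follows the bullet literally will interrupt drug for mild, expected events. A site that reads it as part of an enzyme work-up will not. Both can point to text in the protocol. The trial is open-label and single-arm, with three sites named in 4.1, so there is no control group against which such differences could be judged.

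Three things are at stake: how much drug children have received by the Week 12 ALT measurement, who qualifies for the per-protocol set, and what the tolerance and compliance endpoints in section 3 measure. Section 2.2 names tolerability at 300 mg in children as a critical question of the trial.

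**Working it through.** The point is textual, so the main check applies each rule to one case: a child with a single mild episode of nausea and with ALT, AST, bilirubin and INR unchanged from baseline.

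| Place | Condition in the text | Result for this child |
|---|---|---|
| 8.3.10, opening | ALT or AST > 2 times, or bilirubin > 1.5 times, baseline | No repeat testing |
| 8.3.10, bullets 1 to 3 | ALT or AST > 5, > 3 or > 2 times baseline, the last with bilirubin or INR | No stop |
| 8.3.10, bullet 4 | Any one listed sign | Stop or interrupt |
| 8.2, evaluation | ALT > 2 times baseline with hepatitis symptoms, or > 3 times with or without | No evaluation |
| 8.2, drug stop | Hepatitis signs or symptoms, or ALT > 5 times baseline | Unclear: the signs are not defined |
| 10.1.2 | Grade 3 and probably or possibly related, or grade 4 or higher | No stop required |

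Only bullet 4 clearly requires action. 8.2 depends on whether isolated nausea counts as a sign of hepatitis, and the other rules are silent.

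**Does the plan's design figure change?** Inputs from 9.2: 36 completers, effect size 20/40 = 0.5, two-sided 0.05, Wilcoxon test. Using the noncentral t with n scaled by 3/π, 36 × 0.955 = 34.4, power is 81.2%; simulating the signed-rank test gives 81.5%. The plan states 81%. Enrolment: 36/(1 − 0.10) = 40, as stated. Both figures reproduce, and neither depends on this bullet.

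**Who leaves the primary analysis?** Section 7.1 says that stopping drug is not leaving the study. Section 9.4.2 keeps children whether or not they took the drug and excludes only those with no Week 12 value. Interruption alone therefore removes nobody. What changes is exposure.

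**How many children could be affected?** The documents give no rate for these signs. As an assumption only, if a proportion p of the 40 enrolled had any listed sign while on drug, 40 × p would be interrupted under the literal reading: 2, 4, 8 or 12 children for p = 5%, 10%, 20% or 30%. These are interruptions, not drop-outs.

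**How long must an interruption be to matter elsewhere?** Reading the example criterion in 9.3 as drug taken on at least 80% of days: 12 × 7 = 84 days and 0.80 × 84 = 67.2, so 68 days are needed and up to 84 − 68 = 16 can be missed. Section 7.2 lets the investigator withdraw a child at 14 days or more ("Participant unable to receive gemcabene for" that period). A break of a few days does neither by itself.

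**The case against.** The strongest reply is context. This is a liver-injury plan that opens with enzyme and bilirubin rises and bases the decision on factors including them. An investigator can reasonably read the list as applying to children already in that work-up. This stands as a plausible reading, but the bullet says any subjects and carries no such limit, while its three neighbours spell theirs out. Two defensible readings of a mandatory rule are the defect.

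A cautious trigger may also be intended. The amendment history says the section was added at FDA request, and 2.3.1 says juvenile toxicity studies are not complete. Nor does 10.1.2 forbid stopping at a lower grade. These points stand, and are why the plan should say which reading is meant rather than be presumed wrong.

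The contrast with 8.2 is limited too: its stop sentence also lets symptoms act alone. The difference is a named list against an undefined reference to hepatitis.

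A reader might infer several stronger things that the documents do not support:

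- **That children with asthma or allergy would be stopped for eosinophils.** Criterion 17 does admit some of them (daily prescription medication is "excluded except for allergy medications, ADHD medications, asthma medications"), but nothing says their eosinophils are expected to exceed 5%. Table 2 schedules no blood count at Baseline, Week 2 or Week 6. The scheduled counts are at Screening, Week 12, early termination and follow-up, so this item has little reach during dosing unless an unscheduled count is done.
- **That fatigue is a listed common drug effect.** The documents list asthenia, described as a feeling of weakness. Nausea is listed by name and is enough for the point.
- **That interruptions use up the 10% drop-out allowance or lower the stated power.** They do not, for the reasons in 7.1 and 9.4.2.

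**Conclusion.** The point holds as an unreconciled rule. Bullet 4 of 8.3.10 requires at least a temporary interruption for a single listed sign of any severity or cause. It does not match the framing of its own section, the trigger in 8.2 or the grade and causality rule in 10.1.2. Permanent stopping is not required, because the lead-in allows interruption and sets no minimum length.

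The size cannot be computed from the documents. The range of 2 to 12 interrupted children out of 40 rests entirely on assumed rates of 5% to 30% and on literal application. There is no effect on the size of the observed-case ITT primary analysis unless a child is withdrawn or has no Week 12 value. The effects that remain are partial exposure in some Week 12 ALT values, possible loss from the per-protocol set after long interruptions, and tolerance and compliance results that partly reflect how each site read the bullet. This should be fixed, but it does not undermine the primary analysis.

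**What to change.** Reconcile bullet 4 with the rest of 8.3.10, with 8.2 and with 10.1.2. State in 8.3.10 whether the symptom and eosinophil list applies on its own or only together with an enzyme elevation, and use the same wording in 8.2. If it is meant to stand alone, say how it fits with the common adverse events in 2.2 and 2.3.1, with symptoms present before dosing, and with the grade and causality rule in 10.1.2. Which clinical rule applies is for the sponsor's advisers and the DSMB to decide; this review proposes none.

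The cost is a wording amendment with IRB approval and FDA notification. It needs no new visits, tests or participants, and no change to the sample size or the primary analysis.
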